- 2.2.2 Subject Questionnaire 1: The questionnaire will include statements about the BGMS instructions for use (product labeling) and ease of use of the basic blood testing operations of the meter system. These statements will be given a rating by all of the subjects (1=strongly disagree, 2=disagree, 3=neutral, 4=agree, 5=strongly agree), and frequency distributions will be tabulated. Results will be compared to the following criteria:
- **Acceptance criteria: At least 90% of the applicable statement responses from the questionnaire must be ≥ 3 to pass*.**

Study objectives 2.3.1 and 2.3.4 below are in accordance with **ISO 15197:2013, Section 8**, and apply to data collected **ONLY** from **subjects who have diabetes**. Objectives 2.3.2 and 2.3.3 also apply to subjects who have diabetes. The objectives apply to both CONTOUR NEXT and CONTOUR TV3 BGMS, and the results from the two meter systems will not be compared to each other.

2.3 Secondary Objectives, only subjects with diabetes:

- 2.3.1 Fingerstick Test: Obtain BGMS performance data in the hands of lay users with diabetes using fingerstick capillary blood obtained with Microlet NEXT lancing device.
- **95% of glucose results shall fall within ± 15 mg/dL of laboratory method at glucose concentration < 100 mg/dL and within $\pm 15\%$ at glucose concentrations ≥ 100 mg/dL**
- 2.3.2 Alternative Site Test (AST): Obtain BGMS performance data in the hands of lay users with diabetes using capillary blood from the palm site obtained with Microlet NEXT lancing device with the AST endcap. Acceptance criteria will be the same as fingerstick 2.3.1.
- 2.3.3 Venous Blood Test: Obtain BGMS performance data using venous blood from lay users with diabetes. Acceptance criteria will be the same as fingerstick 2.3.1.
- 2.3.4 Subject Questionnaire 1: The questionnaire will include statements about the BGMS instructions for use (product labeling) and ease of use of the basic blood testing operations of the meter system. These statements will be given a rating by the subjects with diabetes (1=strongly disagree, 2=disagree, 3=neutral, 4=agree, 5=strongly agree), and frequency distributions will be tabulated. Results will be compared to the following criteria:

*This is a “total population” (hypothesis test) requirement for the pool of all subjects.

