- **Acceptance criteria: There must be at least a 90% probability that a user would respond with a score of 3 or higher to statements concerning instructions for use or ease of use.****

Study objectives 2.4 below are internal objectives and apply to data collected from all subjects OR subjects who have diabetes, as specified for each objective. The objectives apply to CONTOUR NEXT and CONTOUR TV3 BGMS as noted, and the results from the two meter systems will not be compared to each other.

2.4 Secondary Objectives (internal objectives):

2.4.1 Fingerstick Test (only subjects with diabetes): Obtain BGMS performance data in the hands of lay users with diabetes using fingerstick capillary blood obtained with Microlet NEXT lancing device.

CONTOUR NEXT:

- **95% of glucose results shall fall within ± 10.5 mg/dL of laboratory method at glucose concentrations < 100 mg/dL and within $\pm 10.5\%$ at glucose concentrations ≥ 100 mg/dL****

CONTOUR TV3:

- **95% of glucose results shall fall within ± 12.5 mg/dL of laboratory method at glucose concentrations < 100 mg/dL and within $\pm 12.5\%$ at glucose concentrations ≥ 100 mg/dL****

2.4.2 Study staff test (both BGMS; two analyses, one for all subjects and one for only subjects with diabetes): Obtain BGMS performance data in the hands of trained study staff testing subjects' fingerstick blood obtained with Microlet NEXT lancing device.

- **95% of glucose results shall fall within ± 15 mg/dL of laboratory method at glucose concentrations < 100 mg/dL and within $\pm 15\%$ at glucose concentrations ≥ 100 mg/dL*,****

2.4.3 Subject Questionnaire 2 (both BGMS; only subjects with diabetes): This questionnaire for subjects with diabetes will include statements about user preferences and feedback regarding the features of the BGMS in routine diabetes management. These statements will be given a rating by the subjects (1=strongly disagree, 2=disagree, 3=neutral, 4=agree, 5=strongly agree), and frequency distributions will be tabulated.

- **Acceptance criteria: There are no pass/fail criteria for Questionnaire 2.**

**This is a "total population" (hypothesis test) requirement for the pool of all subjects with diabetes.

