11.1 Accuracy Objectives

Primary Objective – Accuracy with All Subjects Included

Let MeterBG = meter blood glucose result;

LabBG = laboratory method (YSI) comparator blood glucose result.

For the primary accuracy objective, a result (MeterBG) is considered accurate if:

$$|RD| = 100 * |MeterBG - LabBG| / LabBG \leq 15\%, \text{ regardless of the value of LabBG.}$$

With $n = 350$ evaluable results, $X_c = 333$ results would be required to satisfy the accuracy criteria. At $P_0 = 96.65\%$, there is approximately a 95% chance of satisfying the primary objective. Conversely, at $P_a = 92.81\%$, there is approximately a 95% chance of failing to satisfy this accuracy objective.

In addition to the $\pm 15\%$ accuracy definition, at least 99% of the $n = 350$ fingerstick results must satisfy:

$$|RD| = 100 * |MeterBG - LabBG| / LabBG \leq 20\%, \text{ regardless of the value of LabBG.}$$

Thus at least 347 out of $n = 350$ results must satisfy the $\pm 20\%$ accuracy definition.

With $n = 350$ evaluable results, $X_c = 347$ results would be required to satisfy the accuracy criteria. At $P_0 = 99.61\%$, there is approximately a 95% chance of satisfying this objective. Conversely, at $P_a = 97.80\%$, there is approximately a 95% chance of failing to satisfy this accuracy objective.

Secondary Objectives

Assume 315 evaluable results from people with diabetes. The ISO 15197:2013 acceptance criterion is that 95% of those evaluable results must satisfy the accuracy criteria:

$$|D| = |MeterBG - LabBG| \leq 15 \text{ mg/dL, for LabBG} < 100 \text{ mg/dL}$$

or

$$|RD| = 100 * |MeterBG - LabBG| / LabBG \leq 15\%, \text{ for LabBG} \geq 100 \text{ mg/dL.}$$

With $n = 315$, $X_c = 300$ results would be required to satisfy the accuracy criteria. At $P_0 = 96.79\%$, there is approximately a 95% chance of satisfying the primary objective. Conversely, at $P_a = 92.77\%$, there is approximately a 95% chance of failing to satisfy this objective.

Secondary Objective –Internal Requirements

1. $\pm 10.5\%$ or $\pm 10.5\text{mg/dL}$ (CONTOUR NEXT)

The hypothesis:

$$H_0: \Pr\{|\text{RD}| \leq 10.5\% \text{ when YSI} \geq 100\text{mg/dL or } |\text{D}| \leq 10.5\text{mg/dL when YSI} < 100\text{mg/dL}\} < 0.95$$

Will be tested against the alternative:

$$H_1: \Pr\{|\text{RD}| \leq 10.5\% \text{ when YSI} \geq 100\text{mg/dL or } |\text{D}| \leq 10.5\text{mg/dL when YSI} < 100\text{mg/dL}\} \geq 0.95$$

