With $n = 315$, the critical number of “successes” is $X_c = 294$. That is, at least 294 out of $n = 315$ results must satisfy the requirement:

$$|\text{RD}| \leq 10.5\% \text{ when YSI} \geq 100\text{mg/dL or } |\text{D}| \leq 10.5\text{mg/dL when YSI} < 100\text{mg/dL}$$

This acceptance criterion (critical value) gives about a 92.62% chance of rejecting H_0 in favor of H_1 if the actual probability of “success” is 0.95.

2. $\pm 12.5\%$ or $\pm 12.5\text{mg/dL}$ (CONTOUR TV3)

The hypothesis:

$$H_0: \Pr\{|\text{RD}| \leq 12.5\% \text{ when YSI} \geq 100\text{mg/dL or } |\text{D}| \leq 12.5\text{mg/dL when YSI} < 100\text{mg/dL}\} < 0.95$$

Will be tested against the alternative:

$$H_1: \Pr\{|\text{RD}| \leq 12.5\% \text{ when YSI} \geq 100\text{mg/dL or } |\text{D}| \leq 12.5\text{mg/dL when YSI} < 100\text{mg/dL}\} \geq 0.95$$

With $n = 315$, the critical number of “successes” is $X_c = 294$. That is, at least 294 out of $n = 315$ results must satisfy the requirement:

$$|\text{RD}| \leq 12.5\% \text{ when YSI} \geq 100\text{mg/dL or } |\text{D}| \leq 12.5\text{mg/dL when YSI} < 100\text{mg/dL}$$

This acceptance criterion (critical value) gives about a 92.62% chance of rejecting H_0 in favor of H_1 if the actual probability of “success” is 0.95.

3. Study Staff Test

Two tests of the hypotheses will be performed.

The hypothesis:

$H_0: \Pr\{|\text{RD}| \leq 15\% \text{ when YSI} \geq 100\text{mg/dL} \text{ or } |\text{D}| \leq 15\text{mg/dL} \text{ when YSI} < 100\text{mg/dL}\} < 0.95$

will be tested against the alternative:

$H_1: \Pr\{|\text{RD}| \leq 15\% \text{ when YSI} \geq 100\text{mg/dL} \text{ or } |\text{D}| \leq 15\text{mg/dL} \text{ when YSI} < 100\text{mg/dL}\} \geq 0.95$

One test will be done using data from all subjects, and another using data only from PWD subjects. In the case of all subjects, if $n = 350$, the critical value is 327. For PWD subjects only, if $n = 315$, the critical value is 294. As in all cases, critical values may require adjustment due to differences in sample sizes. The critical values are chosen so that the least upper bound on the probability of passing under minimally acceptable conditions is 95%.

Table 11.1 summarizes critical values for satisfying objectives described in section 2. The column labeled P_o is the minimally acceptable condition (probability) for each objective listed.

Table 11.1 Sample Sizes and Critical Values for Satisfying Objectives

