Objective	Sample Size, n	Critical Value, Xc	Po	Derivation of Critical Value*
2.1.1(95%), 2.2.1	350	333	96.65%	95% of n
2.1.1(9%)	350	347	99.61%	99% of n
2.3.1, 2.3.2, 2.3.3	315	300	96.79%	$\Pr\{\text{PASS} X_c, P_o\} \approx 95\%$
2.4.1	315	294	95.00%	$\Pr\{\text{PASS} X_c, P_o\} \approx 95\%$
2.4.2 (all subjects)	350	327	95.00%	$\Pr\{\text{PASS} X_c, P_o\} \approx 95\%$
2.4.2 (PWDs)	315	294	95.00%	$\Pr\{\text{PASS} X_c, P_o\} \approx 95\%$
2.2.2 (Questionnaire 1, All Subjects)	350	307	90.00%	$\Pr\{\text{PASS} X_c, P_o\} \approx 95\%$
2.3.4 (Questionnaire 1, PWDs)	315	276	90.00%	$\Pr\{\text{PASS} X_c, P_o\} \approx 95\%$
*Critical Values may change depending on actual sample size				

Note that error distribution tables will be constructed, to reflect the numbers and percentages of results falling within various error ranges (e.g., $\pm 5\%$, $\pm 7\%$, $\pm 10\%$, $\pm 12.5\%$, $\pm 15\%$, $\pm 20\%$). Tables will be by clinical site and overall.

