A BGMS result will be considered an “outlier” if its corresponding studentized residual is outside the interval $(\Phi^{-1}(0.005), \Phi^{-1}(0.995)) \approx (-2.576, +2.576)$, corresponding to a 99% interval for a standard normal variate. By this statistical definition of “outlier”, results that may satisfy accuracy requirements may be considered “outliers”.

Confidence bands (95% and 99%) for the regression line will be computed. Scatter plots of MeterBG vs. LabBG will be constructed, with the regression line, the confidence bands, and the line of identity ($Y = X$) will all be plotted. Outliers will be identified.

Error Grid Analyses

Parkes consensus error grids will be constructed for combined strip lots, and combined sites as described in Tables 11.2 and 11.3. There are no criteria for percentages of values within the error grid zones.

Data Analysis Schemes

Table 11.2 Data Analysis Scheme (per ISO 15197:2013)

Blood Type	Data Comparison	Regression Tables	Bland Altman Plots	Accuracy	Error Grid	Error Interval tables (5, 10, 12.5, 15, 20, >20%)
Capillary Fingerstick	Subject vs. YSI	x*	x***	x**	x*	x*
	Staff vs YSI	x*	x***	x**	x*	x*
AST (Palm)	Subject vs. YSI	x*	x***	x**	x*	x*
Venous	Results vs. YSI	x*	x***	x**	x*	x*

* Combined sites

** By site and combined sites

*** Plots with different symbols denoting the site, and whether observations are outliers

Table 11.3 Data Analysis Scheme (per FDA SMBG: 2016)

Blood Type	Data Comparison	Regression Tables	Scatter Plots	Accuracy	Error Grid	Error Interval tables (5%, 7%, 10%, 15%, 20, >20%)
Capillary Fingerstick	Subject vs. YSI	x*	x****	x**	x*	x*
	Staff vs YSI	x*	x****	x**	x*	x*
AST (Palm)	Subject vs. YSI	x*	x****	x**	x*	x*

* Combined sites

** By site and combined sites

*** Plots with different symbols denoting the site, and whether observations are outliers

Note: Samples outside +/- 20% will be identified and listed in the statistics report (per FDA SMBG: 2016).

11.3 Subject Questionnaires 1 and 2

Subject questionnaires 1 and 2 will consist in part of questions/statements for which a numerical score or rating (1=strongly disagree, 2=disagree, 3=neutral, 4=agree, 5=strongly agree) will be provided by the subjects and entered by the study staff. For these numerically-scored questions, frequency distributions will be tabulated.

For Questionnaire 1 only:

Hypothesis tests for selected statements will be performed. The hypotheses are:

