$$H_0: Pr\{response \geq 3\} < 90\% \text{ versus the alternative:}$$

$$H_a: Pr\{response \geq 3\} \geq 90\%$$

The critical number of responses greater than or equal to 3, X_c , is a function of the actual sample size, and will be chosen such that $0.95 = \sup Pr\{X \geq X_c | 100p\% = 90\%\}$. For example, if $n = 350$, then $X_c = 307$, so that $Pr\{X \geq X_c | 100p\% = 90\%\} \approx 0.9316 \leq 0.95$. That is, 307 is the number of responses ≥ 3 which yields the largest value of $Pr\{X \geq X_c | 100p\% = 90\%\} \leq 0.95$ for $n = 350$. For $n = 315$, the critical value is $X_c = 300$ (power ≈ 0.95).

11.4 Demographic, Diabetes History, Medications and Medical Conditions Data, Questionnaires 1 and 2

Descriptive statistics for Demographics, Diabetes History, Medications and Medical Conditions, and subject questionnaires will be computed as appropriate. Histograms will be constructed where appropriate. A percentage of subjects < 65 years of age will be calculated.

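### Objectives 2.2.2, 2.3.4, 2.4.1 and 2.4.2 state their hypotheses the wrong way round for their critical values, and Questionnaire 1 at n = 315 has two critical values (276 and 300)

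*Combined protocol and SAP*

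**What the plan says.** Section 11.1 (Internal Requirements and Study Staff Test) states H0 as a success probability below 0.95 and H1 as 0.95 or more. Section 11.3 does the same for Questionnaire 1 with 90%, where "Hypothesis tests for selected statements will be performed". The Section 2 footnotes, and the hypotheses in 11.1 and 11.3, make all four objectives hypothesis-test requirements on a population.

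The thresholds follow one rule. Section 11.1 words it as: "The critical values are chosen so that the least upper bound on the probability of passing under minimally acceptable conditions is 95" per cent. Section 11.3 gives the same rule as a formula: choose the count whose pass probability at a true 90% is the largest that does not exceed 0.95. Table 11.1 lists the results:

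- 294/315 for 2.4.1 and for 2.4.2 in subjects with diabetes
- 327/350 for 2.4.2 in all subjects
- 307/350 for 2.2.2
- 276/315 for 2.3.4

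Of 294/315, Section 11.1 says: "This acceptance criterion (critical value) gives about a 92.62% chance of rejecting" H0 in favour of H1 when the true probability is 0.95.

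For Questionnaire 1 at n = 315, Section 11.3 says "the critical value is $X_c = 300", with power of about 0.95. Table 11.1 has 276 for the same test at the same n.

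**The concern.** A test that rejects H0: p < 0.95 is normally expected to have a small chance of doing so when p is just under 0.95. Here the plan makes that chance as large as it can, up to 95%. A threshold built that way suits the opposite question, in which the product is presumed to meet 95% and fails only on evidence against it. The two readings support different claims. As written, the report could say that accuracy of at least 95% (or a favourable response rate of at least 90%) had been established by rejecting H0, when the data were merely compatible with it.

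The second problem is a plain conflict. Objective 2.3.4 is pass/fail, and two sections set thresholds 24 responses apart for the same n. Whoever writes the report would have to choose between them, possibly after seeing the counts.

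**Working it through.** **Inputs.** Hypotheses, n and critical values Xc from Sections 11.1 and 11.3 and Table 11.1. Boundary Po = 0.95 for accuracy and 0.90 for Questionnaire 1 (Table 11.1).

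**Formula.** P(pass | p) = P(X ≥ Xc), with X ~ Binomial(n, p). This is continuous and increasing in p, so its supremum over H0: p < Po is its value at p = Po.

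**Step 1: reproduce the plan's figures.** P(X ≥ 294 | 315, 0.95) = 0.9263, against a stated 92.62%. P(X ≥ 307 | 350, 0.90) = 0.9316, as stated.

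**Step 2: confirm the rule and read off the type I error.** The rule takes the smallest Xc with P(pass | Po) ≤ 0.95.

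| Objective | Xc/n | Xc as % of n | P(pass at Po) | Same with Xc − 1 |
|---|---|---|---|---|
| 2.4.1; 2.4.2 (diabetes) | 294/315 | 93.3% | 0.9263 | 0.9536 |
| 2.4.2 (all) | 327/350 | 93.4% | 0.9246 | 0.9514 |
| 2.2.2, per statement | 307/350 | 87.7% | 0.9316 | 0.9510 |
| 2.3.4, per statement | 276/315 | 87.6% | 0.9299 | 0.9506 |

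All four Table 11.1 values obey the rule. The fourth column is the supremum of the type I error under H0 as printed. Each minimum passing proportion lies below the level said to be shown.

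**Step 3: pass probability inside the stated H0.**

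| True rate | 294/315 | 327/350 |
|---|---|---|
| 94% | 0.738 | 0.721 |
| 93% | 0.464 | 0.428 |
| 92% | 0.225 | 0.189 |

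| True rate, per statement | 307/350 | 276/315 |
|---|---|---|
| 88% | 0.605 | 0.624 |
| 87% | 0.382 | 0.412 |

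**Step 4: compare with the plan's own intervals.** Section 11.2 specifies two-sided 95% Clopper-Pearson intervals. At the minimum passing counts the lower limits are 90.0% (294/315), 90.3% (327/350), 83.8% (307/350) and 83.5% (276/315).

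**Step 5: 276 or 300.** At n = 315 and a true 90%, 276 gives 0.930 and 275 gives 0.951, so the rule in Section 11.3 selects 276. With 300 the pass probability is 0.0005. P(X ≥ 300 | 315, p) reaches 0.950 at p = 0.9679, and 300 with Po = 96.79% is the Table 11.1 entry for objectives 2.3.1 to 2.3.3. A carry-over from that row is likely, though the documents do not say so.

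**Step 6: what each repair implies.**

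| Xc/n now | Hypotheses swapped, Xc kept: chance of failing at Po | Hypotheses swapped, at most 5%: Xc | Hypotheses kept, at most 5%: Xc (P(pass at Po)) |
|---|---|---|---|
| 294/315 | 7.4% | 293 (4.6%) | 306 (0.0449) |
| 327/350 | 7.5% | 326 (4.9%) | 340 (0.0353) |
| 307/350 | 6.8% | 306 (4.9%) | 325 (0.0405) |
| 276/315 | 7.0% | 275 (4.9%) | 293 (0.0405) |

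The 5% level is an assumption; the plan states no alpha for these tests.

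**The case against.** The best reply is that this is a labelling slip in a rule whose behaviour is disclosed. The plan prints 92.62% and 0.9316 and calls Po the minimally acceptable condition, so it evidently means a product at Po to pass most of the time. The intervals in Section 11.2 would show readers a lower limit near 90% beside a bare pass. The objectives are secondary, two of them are internal, and the recommended repair changes no value in Table 11.1. The 300 is a single figure at odds with the rule in its own paragraph.

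Most of this is fair, and it limits the severity. The thresholds are a defensible choice once described correctly, and the intervals do help. But disclosure does not repair the hypotheses. The plan describes a pass as rejecting H0 in favour of H1, and that inference is unsupported. The note that critical values depend on the actual sample size does not explain 276 against 300, because both are given for n = 315.

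One caution on size stands. Section 5.13.1 lists six statements under the questionnaire criteria, and the plan does not say whether all must pass. If they must, the chance of passing all six at a true 88% with n = 350 lies between 0.605^6 = 0.049 (independence) and 0.605 (perfect dependence). The questionnaire figures above are therefore per statement only.

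**Conclusion.** Both parts hold. With the hypotheses as printed, the four objectives use tests whose type I error approaches 92 to 93%, so a pass cannot be read as showing at least 95% accuracy or at least 90% favourable responses. The critical values are correctly computed for the reverse hypotheses, under which a pass means that a shortfall was not shown. For objective 2.3.4 the value 300 in Section 11.3 is wrong by that section's own rule, and 276 is consistent with it.

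The figures assume independent results with a common success probability, as the plan's binomial calculations do, and the planned n of 315 and 350. The primary criteria are set as 95% and 99% of n and are not affected, nor are ISO objectives 2.3.1 to 2.3.3. This should be fixed before data are seen, but it does not threaten the main conclusions.

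**What to change.** 1. In Sections 11.1 and 11.3 restate the hypotheses as H0: p ≥ 0.95 (0.90) against H1: p < 0.95 (0.90).
2. Keep the Table 11.1 critical values and describe them as a one-sided test with about a 7% chance of failing at the boundary. If a strict 5% is wanted, lower each value by one.
3. Remove the wording about rejecting H0 in favour of H1, and define a pass as not shown to be below 95% (90%).
4. In Section 11.3 replace 300 and its power of about 0.95 with 276 and a pass probability of about 0.930 at a true 90%.

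This costs some rewording and one number. It needs no extra subjects and, unless the strict 5% is chosen, no change to Table 11.1.

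If the sponsor instead wants to demonstrate at least 95% (90%) at an assumed one-sided 5%, keep the hypotheses and raise the thresholds to 306/315, 340/350, 325/350 and 293/315, which is 12, 13, 18 and 17 more results. A pass chance near 90% on the accuracy tests would then need a true rate of about 98% (0.896 at n = 315, 0.904 at n = 350).

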11.2 Other Statistical Computations

Some data analysis follows analyses and presentations described in ISO Section 15197:2013, Section 8. See Table 11.2 for scheme of data analysis, including capillary fingerstick blood and venous blood.

Other data analysis follows analyses and presentations described in the FDA SMBG: 2016. See Table 11.3 for scheme of data analysis, including capillary fingerstick blood and venous blood per the FDA SMBG:2016.

Linear regression will be performed on data comparisons as shown in Tables 11.2 and 11.3.

Modified Bland-Altman Plots – Modified Bland-Altman plots (difference between evaluation device results and reference results plotted against reference results) will be constructed for all comparisons described in Tables 11.2 and 11.3.

Confidence Intervals

Confidence intervals (95%, two-sided) for all primary and secondary objective proportions (percents) will be computed using the Clopper-Pearson⁵ (1934) formula:

$$P_L = \frac{X * F_{\alpha/2}^{-1}(2X, 2(n - X + 1))}{n - X + 1 + X * F_{\alpha/2}^{-1}(2X, 2(n - X + 1))}$$

and:

$$P_U = \frac{X * F_{1-\alpha/2}^{-1}(2X, 2(n - X + 1))}{n - X + 1 + X * F_{1-\alpha/2}^{-1}(2X, 2(n - X + 1))}$$

P_L = lower limit

P_U = upper limit

X = number of “accurate” results (per the relevant definition of “accurate”)

Regression and Outlier Analysis

A linear regression of the BGMS results against the YSI reference method results via weighted least squares (WLS) will be performed, with weights:

$$W = \frac{1}{YSI^2} \text{ used to account for the proportional variance nature of blood glucose measurements (Draper and Smith, 1998)}^6.$$

Studentized residuals from the regression will be computed, i.e.,

$$e_i = y_i - \hat{y}_i$$

⁵ Clopper, C.J., Pearson, E.S. (1934) The use of confidence or fiducial limits as illustrated in the case of the binomial, *Biometrika*, 26, 404-413

⁶ Draper, N. R., Smith, H., (1998) *Applied Regression Analysis*, 3rd Ed., John Wiley and Sons

$$\varepsilon_i = \frac{e_i}{s_\varepsilon}$$

That is, a studentized residual, ε , is the residual, e , divided by the standard error of residuals, s_ε

$$s_{\varepsilon_i} = \hat{\sigma} \sqrt{1 - h_{ii}}$$

$\hat{\sigma}$ = root mean square error (RMSE) from the regression model.

and h_{ii} is the leverage for the i^{th} observation.

A BGMS result will be considered an “outlier” if its corresponding studentized residual is outside the interval $(\Phi^{-1}(0.005), \Phi^{-1}(0.995)) \approx (-2.576, +2.576)$, corresponding to a 99% interval for a standard normal variate. By this statistical definition of “outlier”, results that may satisfy accuracy requirements may be considered “outliers”.

Confidence bands (95% and 99%) for the regression line will be computed. Scatter plots of MeterBG vs. LabBG will be constructed, with the regression line, the confidence bands, and the line of identity ($Y = X$) will all be plotted. Outliers will be identified.

Error Grid Analyses

Parkes consensus error grids will be constructed for combined strip lots, and combined sites as described in Tables 11.2 and 11.3. There are no criteria for percentages of values within the error grid zones.

Data Analysis Schemes

Table 11.2 Data Analysis Scheme (per ISO 15197:2013)

Blood Type	Data Comparison	Regression Tables	Bland Altman Plots	Accuracy	Error Grid	Error Interval tables (5, 10, 12.5, 15, 20, >20%)
Capillary Fingerstick	Subject vs. YSI	x*	x***	x**	x*	x*
	Staff vs YSI	x*	x***	x**	x*	x*
AST (Palm)	Subject vs. YSI	x*	x***	x**	x*	x*
Venous	Results vs. YSI	x*	x***	x**	x*	x*

* Combined sites

** By site and combined sites

*** Plots with different symbols denoting the site, and whether observations are outliers

Table 11.3 Data Analysis Scheme (per FDA SMBG: 2016)

Blood Type	Data Comparison	Regression Tables	Scatter Plots	Accuracy	Error Grid	Error Interval tables (5%, 7%, 10%, 15%, 20, >20%)
Capillary Fingerstick	Subject vs. YSI	x*	x****	x**	x*	x*
	Staff vs YSI	x*	x****	x**	x*	x*
AST (Palm)	Subject vs. YSI	x*	x****	x**	x*	x*

* Combined sites

** By site and combined sites

*** Plots with different symbols denoting the site, and whether observations are outliers

Note: Samples outside +/- 20% will be identified and listed in the statistics report (per FDA SMBG: 2016).

11.3 Subject Questionnaires 1 and 2

Subject questionnaires 1 and 2 will consist in part of questions/statements for which a numerical score or rating (1=strongly disagree, 2=disagree, 3=neutral, 4=agree, 5=strongly agree) will be provided by the subjects and entered by the study staff. For these numerically-scored questions, frequency distributions will be tabulated.

For Questionnaire 1 only:

Hypothesis tests for selected statements will be performed. The hypotheses are:

$$H_0: Pr\{response \geq 3\} < 90\% \text{ versus the alternative:}$$

$$H_a: Pr\{response \geq 3\} \geq 90\%$$

The critical number of responses greater than or equal to 3, X_c , is a function of the actual sample size, and will be chosen such that $0.95 = \sup Pr\{X \geq X_c | 100p\% = 90\%\}$. For example, if $n = 350$, then $X_c = 307$, so that $Pr\{X \geq X_c | 100p\% = 90\%\} \approx 0.9316 \leq 0.95$. That is, 307 is the number of responses ≥ 3 which yields the largest value of $Pr\{X \geq X_c | 100p\% = 90\%\} \leq 0.95$ for $n = 350$. For $n = 315$, the critical value is $X_c = 300$ (power ≈ 0.95).

11.4 Demographic, Diabetes History, Medications and Medical Conditions Data, Questionnaires 1 and 2

Descriptive statistics for Demographics, Diabetes History, Medications and Medical Conditions, and subject questionnaires will be computed as appropriate. Histograms will be constructed where appropriate. A percentage of subjects < 65 years of age will be calculated.

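### Section 11.2 misprints two formulas: the Clopper-Pearson upper limit is the one for X−1, and the studentized residual of the weighted regression leaves out the weight

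*Combined protocol and SAP*

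**What the plan says.** Under Confidence Intervals, section 11.2 states: "Confidence intervals (95%, two-sided) for all primary and secondary objective proportions (percents) will be computed using the Clopper-Pearson" method. Two F-quantile expressions follow. The lower limit uses multiplier X, offset n−X+1, degrees of freedom (2X, 2(n−X+1)) and the α/2 quantile. The upper limit begins "P_U = \frac{X * F_{1-\alpha/2}^{-1}(2X, 2(n - X + 1" and keeps all of these terms; only the quantile changes, to 1−α/2.

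Under Regression and Outlier Analysis, the same section specifies weighted least squares of meter result on YSI with W = 1/YSI², "used to account for the proportional variance nature of blood glucose measurements". The residual is the observed minus the fitted value, e = y − ŷ. Its standard error is printed as σ̂·√(1−h), where σ̂ is the "root mean square error (RMSE) from the regression model". No weight appears in either. A result is called an outlier when the ratio falls outside ±2.576, "corresponding to a 99% interval for a standard normal variate".

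The flag is carried to the figures: the footnote to Tables 11.2 and 11.3 reads "Plots with different symbols denoting the site, and whether observations are outliers", and the text has outliers identified on the scatter plots. Acceptance is handled separately in section 11.1: "Table 11.1 summarizes critical values for satisfying objectives described in section 2".

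**The concern.** A Clopper-Pearson interval inverts two different binomial tails, so its two limits cannot share the same degrees of freedom with only the quantile swapped. If the printed upper limit is programmed, every reported upper limit for both meters, in all four study reports, is too low. The intervals also lose the guaranteed coverage of at least 95% that defines the named method.

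For the residual, weighting by 1/YSI² puts the RMSE on a relative scale (about 0.05 for a 5% error), while the residual stays in mg/dL. Dividing one by the other without the weight gives a quantity that carries units and grows with glucose. Comparing it with a standard normal cut-off has no meaning, and the outlier marks on the plots would not identify unusual results.

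**Working it through.** The plan gives no numerical confidence limit or outlier count, so the formulas themselves were checked. As background, the pass probabilities in section 11.1 do reproduce: at least 333/350 has probability 0.950 at 96.65%, at least 347/350 has 0.9505 at 99.61%, and at least 300/315 has 0.9502 at 96.79%.

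**(a) Upper confidence limit**

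Inputs: α = 0.05 (section 11.2); n and X from Table 11.1.

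- Printed lower limit: X·F / (n−X+1 + X·F), with F the 0.025 quantile on (2X, 2(n−X+1)) df. At 333/350, F(666, 36) = 0.6513, giving 333 × 0.6513 / (18 + 333 × 0.6513) = 92.34%. This equals the exact lower limit.
- Printed upper limit: the same expression with the 0.975 quantile. At 333/350, F(666, 36) = 1.7032, giving 333 × 1.7032 / (18 + 333 × 1.7032) = 96.92%.
- Exact upper limit: (X+1)·F / (n−X + (X+1)·F), with F the 0.975 quantile on (2(X+1), 2(n−X)) df. At 333/350, F(668, 34) = 1.7321, giving 334 × 1.7321 / (17 + 334 × 1.7321) = 97.15%.

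Replacing X by X−1 in the exact form gives multiplier X, offset n−X+1 and df (2X, 2(n−X+1)), which is the printed form. So the printed limit at X is always the exact limit at X−1. It solves P(count ≤ X−1) = 0.025 instead of P(count ≤ X) = 0.025. At the printed limit for 333/350, the tail that should be 2.5% is 4.5%; for 347/350 it is 9.8%.

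| X/n | Printed upper | Exact upper | Shortfall (points) |
|---|---|---|---|
| 333/350 | 96.92% | 97.15% | 0.22 |
| 347/350 | 99.69% | 99.82% | 0.14 |
| 300/315 | 97.07% | 97.31% | 0.24 |
| 294/315 | 95.57% | 95.83% | 0.25 |
| 327/350 | 95.56% | 95.79% | 0.23 |
| 307/350 | 90.72% | 90.96% | 0.25 |
| 276/315 | 90.77% | 91.05% | 0.275 |
| 350/350 | 99.993% | 100% | 0.007 |

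Two-sided coverage, summed over the binomial distribution:

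| n | True rate | Printed pair | Exact pair |
|---|---|---|---|
| 350 | 0.9665 | 94.9% | 96.2% |
| 350 | 0.9961 | 95.0% | 98.7% |
| 315 | 0.9679 | 96.4% | 97.7% |
| 315 | 0.95 | 94.9% | 96.1% |

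For n = 350 the printed pair falls to 92.6% within the range 0.90 to 0.99 and to 78.8% at 0.99932. Above 0.99993 its coverage is zero, because even 350/350 gives an upper limit below the true rate. The exact pair never falls below 95%. The chance that the upper limit lies below the true rate should be at most 2.5%; with the printed limit at n = 350 it is 2.9% at 0.9665 and 5.0% at 0.9961.

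**(b) Studentized residual**

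Under weighted least squares, Var(e) = σ²(1−h)/W. With W = 1/YSI², the standard error is σ̂·YSI·√(1−h). The printed version lacks the factor YSI.

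Scale check, taking a 5% error (an assumption) and ignoring leverage: at YSI = 150 mg/dL, a one-SD error is 0.05 × 150 = 7.5 mg/dL. As printed, the ratio is 7.5/0.05 = 150; with the weight it is 7.5/(0.05 × 150) = 1. The printed cut-off amounts to |e| > 2.576 × 0.05 = 0.13 mg/dL.

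Simulation with n = 350. Assumed, not in the documents: lognormal YSI with median 150 and log-SD 0.45, limited to 50–450 mg/dL, and 5% CV. Share flagged:

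| Reading of the formula | Overall | Above 250 mg/dL | Below 100 mg/dL |
|---|---|---|---|
| As printed | 98.5% | – | – |
| With the weight | 1.0% | – | – |
| As printed, weights rescaled to mean 1 | 7.4% | 29% | 0.02% |
| RMSE taken as unweighted, in mg/dL | 2.4% | about 13% | 0% |

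Over CV 3–7%, median 130–170 and log-SD 0.40–0.50, the printed form flags 98.3–98.7%. With rescaled weights it flags 6–9% overall, 24–33% above 250 mg/dL and at most 0.1% below 100.

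**The case against.** The case for leaving this alone has real content. No decision depends on either formula: pass/fail is a count against the critical value, outliers are only marked, and section 11.2 itself warns that accurate results may be labelled outliers. The methods are correctly named, and standard software asked for a Clopper-Pearson interval or a studentized residual from a weighted fit would return the right values, so the errors bite only if the printed lines are hand-coded. For criteria of the at-least-95% kind the lower limit is the informative one, and it is exact. The upper-limit error is a fraction of a point, coverage at the plan's own Po values is close to nominal, and 99.993% would print as 100.0% to one decimal. Flagging nearly every point would be noticed at once, and all flag percentages rest on an assumed glucose distribution. Finally, the equations were machine-read from PDF, so a lost term in the residual formula cannot be wholly excluded.

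Most of this stands and bounds the importance of the point. It does not make the formulas right. Correct software output would contradict the stated plan; literal programming would give wrong output. The milder readings of the RMSE are less conspicuous but still misplace the flags, concentrating them at high glucose. The scale mismatch itself needs no distributional assumption. A reading error is an unlikely explanation for the upper limit, because multiplier, offset and degrees of freedom are mutually consistent and recur in numerator and denominator.

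**Conclusion.** Both formulas are wrong as written.

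The upper-limit error follows from algebra alone: the limits are 0.14 to 0.275 points too low at the planned critical values, and guaranteed coverage is lost. Average behaviour at the plan's Po values stays near 95%, with the serious failures at true rates very close to 100%.

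The residual error also follows from algebra. Its practical size depends on the assumed glucose distribution and CV and on how the RMSE is read, from nearly everything flagged to a smaller excess confined to higher glucose. None of the readings without the weight delivers the stated 99% interval.

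Lower limits, critical values, acceptance decisions and the set of evaluable results are unaffected. The text should be corrected before the analysis is programmed, but the point does not threaten the trial's conclusions.

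**What to change.** In section 11.2:

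1. Replace the upper limit by P_U = (X+1)·F / [n−X + (X+1)·F], with F the 1−α/2 quantile on (2(X+1), 2(n−X)) degrees of freedom, and set P_U = 1 when X = n. Leave P_L as it is.
2. Define the studentized residual as √W·e / (σ̂·√(1−h)), equivalently with standard error σ̂·YSI·√(1−h). State that σ̂ is the RMSE of the weighted fit and h the leverage from the weighted hat matrix.

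The cost is two formula corrections and a check that the analysis programs agree with them. Data collection, conduct, sample size, critical values and acceptance criteria do not change.
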